11.5 Interim and final analysis plans

The primary analysis will be intent-to-treat population.

All testing will be stratified by the randomization stratification factors. Tests of the null hypothesis will be done using the log-rank test. Futility analysis testing will be performed using a modified log-rank test modified for testing non-null hypotheses (a score of the alternative hazard ratio).

100% of expected RFS is 536 events. One formal interim analysis of the overall population RFS endpoint is scheduled at approximately 75% of RFS events (402 RFS events calculated across both arms under the alternative). At the interim analysis, an efficacy test will be done (test of null hypothesis $HR=1$) with a one-sided alpha=0.09%. At the interim analysis a futility test will evaluate if the HR from a Cox regression model stratified by the randomization factors favors the control arm ($HR>1$). If an efficacy or futility boundary is crossed at the interim analysis, the DSMC will consider early release of the RFS results. The final analysis of the overall population RFS will test of the null hypothesis ($HR=1$) at the two-sided 0.32% level (one-sided 0.16% level) in order to account for the interim analysis.

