Up to two formal interim analyses of the overall population OS will be completed at approximately 55% and 80% events (206 and 399 events, respectively, events calculated across both arms under the alternative). At both interim analyses, an efficacy test will be done (test of null hypothesis $HR=1$) with a one-sided alpha=0.125%. At the first interim analysis a futility test will evaluate if the HR from a Cox regression model stratified by the randomization factors favors the control arm ($HR>1$). At the second interim analysis a futility test will be done testing the alternative hazard ratio ($HR=0.73$) with a one-sided alpha of 2.5%. If a boundary for futility is crossed at an interim analysis, the DSMC will consider the toxicities on each arm. Considering the magnitude of the survival difference between the two arms along with the relative toxicities, the DSMC can choose not to recommend reporting results early if additional data on the potential non-inferiority of pembrolizumab is warranted. The final analysis of the overall population OS will test of the null hypothesis ($HR=1$) at the two-sided 3.6% level (one-sided 1.8% level) in order to account for interim analyses. At the final analysis for the overall population OS, a two-sided test of the null hypothesis of OS in the PD-L1 positive subgroup will be performed at the two-sided alpha=1.52% level² (one-sided 0.76% level).

The final OS superiority test will be performed in a stepwise fashion following an OS non-inferiority test using a margin of 1.045. An upper limit of a one-sided 98.15% confidence interval less than 1.045 will be considered evidence of non-inferiority of pembrolizumab compared to the control arm.

At the final analysis for OS, results for RFS with updated follow-up will be presented. We note that because of the expected survival patterns with this population, the average hazard ratio is expected to become more null (closer to 1) over time. Under the alternative hypothesis, at 3.5 years since the first patient is randomized the hazard ratio is 0.70, while at 5 years since the first patient is randomized the hazard ratio is 0.73.

There will be no formal interim testing of RFS (overall or PD-L1 positive subgroup) or of OS in the PD-L1 positive subgroup.

If 100% RFS or OS events has not been reached by 3.5 years after the last eligible patient is randomized, the final RFS and OS analyses will be performed at this time.

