¹ Alpha to be calculated based on observed proportion of total OS events in the PD-L1 positive group.

The sample size of this trial was determined to ensure appropriate power to detect meaningful OS differences. As such, the trial is overpowered for RFS, and may therefore detect small RFS differences of uncertain clinical benefit. Hence, regardless of the statistical significance of the RFS results, the clinical benefit of pembrolizumab will be

assessed by the magnitude of the relative and absolute RFS improvement of the pembrolizumab arm over the control arm, and by the comparisons of overall survival and toxicity between the treatment arms.

Under this design and assuming PD-L1 positive patients have the same OS on the control arm as the whole population, the alternative OS survival model for 80% power is model is written that OS at year t is equal to $0.44+0.56\exp(-0.13t)$ [44% long-term survivors and median OS of 5.3 years for non-long-term survivors]. This corresponds to an average HR of 0.58 from a Cox proportional hazards model at 100% OS events. The alternative OS survival model for 90% power is model is written that OS at year t is equal to $0.45+0.55\exp(-0.13t)$ [45% long-term survivors and median OS of 5.3 years for non-long-term survivors]. This corresponds to an average HR of 0.56 from a Cox proportional hazards model at 100% OS events.

Design properties were determined via simulation with 100,000 replications. Properties of the design are summarized in the tables below.

Table 1 Overall population OS Interim and final analysis summary. Events calculated across both arms. Actual analysis timing may vary.

Percent OS events	Study Year	N events	Tests done
55%	3	206	Efficacy and futility
80%	4	299	Efficacy and futility
100%	5	374	Efficacy

Table 2 Characteristics of interim and final overall population OS analyses

OS Scenario	Probability under alternative	Probability under null
Probability stop for futility at 1 st interim analysis	1%	50%
Probability stop for efficacy at 1 st interim analysis	28%	<1%
Probability stop for futility at 2 nd interim analysis	1%	17%
Probability stop for efficacy at 2 nd interim analysis	19%	<1%
Probability stop early for futility	2%	67%
Probability stop early for efficacy	48%	1%
Probability of positive result	86%	2.1% ^a

^a Ignoring futility monitoring two-sided, alpha level=3.7%

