Table 3 Overall population RFS Interim and final analysis summary. Events calculated across both arms. Actual analysis timing may vary.

Percent RFS events	Expected time	N events	Tests done
75%	Mid-2018	402	Efficacy and futility
100%	Late 2018	536	Efficacy

Table 4 Characteristics of interim and final overall population RFS analyses

RFS Scenario	Probability under alternative	Probability under null
Probability stop for futility at interim analysis	<1%	50%
Probability stop for efficacy at interim analysis	69%	<1%
Probability of positive result	90%	0.22% ^a

^a Ignoring futility monitoring two-sided, alpha level=0.4%

Table 5 Additional characteristics of overall population OS analyses. Events calculated across both arms. Actual analysis timing may vary.

Analysis	Alpha level	HR threshold	OS Events
Year 3 interim efficacy	0.125% (one-sided)	0.67	206
Year 3 interim futility	NA	1	206
Year 4 interim efficacy	0.125% (one-sided)	0.70	299
Year 4 interim futility	2.5%	0.92	299
Year 5 final efficacy	3.6% (two-sided)	0.81	374

HR threshold = HR that will correspond to a significant p-value based on alpha level. For efficacy analyses HRs less than the threshold will be significant, for futility analyses HRs larger than the threshold will warrant early closure of the study.

Table 6 Characteristics of overall population RFS analyses. Actual analysis timing may vary.

Analysis	Alpha level	HR threshold	RFS Events
interim efficacy	0.09% (one-sided)	0.66	402
Interim futility	NA	1	402
Final efficacy	0.32% (two-sided)	0.78	536
Year 5 follow-up	NA	NA	668

HR threshold = HR that will correspond to a significant p-value based on alpha level. For efficacy analyses HRs less than the threshold will be significant.

Table 7 PD-L1 positive subgroup analysis details, N = 596 (48.2% prevalence)*

Endpoint	Time point	Alpha-level (two sided)*	HR threshold	Design HR	Power
OS	Year 5	1.52%	0.66	0.57	80%
OS	Year 5	1.52%	0.68	0.56	90%

* These calculations assume a 48.2% event fraction in the PD-L1 positive subgroup. For the final analysis, calculations will be based on the observed fraction of events in the trial. HR threshold = HR that will correspond to a significant p-value based on alpha level. Design HR = HR that provides stated level of power.

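### Section 11.5 both schedules and rules out the overall-population RFS interim, and Table 6's interim HR threshold of 0.66 should be about 0.73

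*Combined protocol and SAP*

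**What the plan says.** **The interim is planned.** Section 11.5 states: "One formal interim analysis of the overall population RFS endpoint is scheduled at approximately 75% of RFS events". It sets that look at 402 of 536 events, with an efficacy test at one-sided 0.09% and a futility check on whether the stratified Cox HR exceeds 1. The consequence is also stated: "If an efficacy or futility boundary is crossed at the interim analysis, the DSMC will consider early release of the RFS results". The final RFS test is set at 0.32% two-sided (0.16% one-sided) "in order to account for the interim analysis". Table 3 lists the look as "75% Mid-2018 402 Efficacy and futility", Table 4 gives a 69% chance of crossing for efficacy there under the alternative, and Table 6 gives its alpha, HR threshold (0.66) and events.

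**The interim is ruled out.** Further on in Section 11.5: "There will be no formal interim testing of RFS (overall or PD-L1 positive subgroup) or of OS in the PD-L1 positive subgroup".

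**What the threshold means.** The note to Table 6 defines the HR threshold as the hazard ratio at which the test just reaches significance at that row's alpha. The column is therefore derived from alpha and events and is not a separate rule.

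**The concern.** RFS in the overall population is one of three primary objectives. As written, Section 11.5 supports three different instructions for the same look: test at one-sided 0.09%, require an observed HR below 0.66, or do not test at all.

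The value 0.66 also looks wrong beside its neighbour in Table 6. The final threshold is 0.78 at 536 events. With 75% of the events already in, and one-sided alpha moving only from 0.16% to 0.09%, a drop to 0.66 is far too large. A monitoring committee that read the HR column as the boundary would treat an observed HR of 0.70, the design value, as not crossing, although the specified log-rank test would be significant.

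**Working it through.** **1. The two statements.** The word *overall* in the later sentence leaves no reading under which both hold. The alphas show which was intended. Section 11.4 allocates 0.4% two-sided (0.2% one-sided) to RFS. With one-sided 0.09% at 402 events and 0.16% at 536, and correlation √(402/536) = 0.866 between the two test statistics, a bivariate normal gives a total one-sided type I error of 0.206% (0.198% to 0.214% allowing for rounding of the two alphas). That agrees with the 0.2% allocation. Without the interim there would be no reason to lower the final alpha.

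**2. The thresholds.** With 1:1 allocation the critical HR is exp(-2z/√events), where z is the normal quantile for the one-sided alpha. The formula is checked first on the other rows of Tables 5 and 6. For the second OS interim I use the 299 events of Tables 1 and 5, which is 80% of 374; the text of 11.5 prints 399.

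| Row | One-sided alpha | Events | Computed | Printed |
|---|---|---|---|---|
| OS first interim | 0.125% | 206 | 0.656 | 0.67 |
| OS second interim | 0.125% | 299 | 0.705 | 0.70 |
| OS final | 1.8% | 374 | 0.805 | 0.81 |
| RFS final | 0.16% | 536 | 0.775 | 0.78 |
| **RFS interim** | **0.09%** | **402** | **0.732** | **0.66** |

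The second-interim OS futility bound also agrees: 0.73 × exp(1.96 × 2/√299) = 0.916, printed 0.92. The largest gap elsewhere is 0.014 (OS first interim). The RFS interim gap is 0.07.

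**3. Other readings of 0.66.**
- Rounding of the alpha (0.085% to 0.095%) gives 0.731 to 0.734.
- Reading 0.09% as two-sided gives 0.718.
- The Freedman form (1-k)/(1+k), with k = z/√events, gives 0.731.
- The linear form 1-2z/√events gives 0.689, or 0.669 with a two-sided alpha, and it fails the RFS final row (0.745 against 0.78).

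In the other direction, HR 0.66 at 402 events has z = -ln(0.66) × √402/2 = 4.166, a one-sided p of 0.0000155. At 0.09%, 0.66 would be the threshold at about 4 × (3.121/0.4155)² ≈ 226 events.

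**4. How often the difference matters.** At a fixed HR of 0.70 and 402 events, the normal approximation gives a 67.5% chance of crossing the 0.09% test and a 28% chance of HR below 0.66, so about 40% lies between.

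I also simulated the RFS models in Section 11.3: control 0.35 + 0.65·exp(-0.67t) against pembrolizumab 0.41 + 0.59·exp(-0.48t). Inputs were 1,240 patients, 2.5 years of accrual, no dropout, an unstratified analysis and 8,000 trials (Monte Carlo standard error about 0.5 points).

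| | Uniform accrual | Ramped accrual |
|---|---|---|
| Mean HR at 402 / 536 events | 0.685 / 0.698 | 0.681 / 0.696 |
| Significant at 0.09% | 75.7% | 77.9% |
| HR below 0.66 | 37.7% | 39.6% |
| Significant but HR above 0.66 | 38.0% | 38.3% |
| Overall power, 0.09% test / 0.66 bound | 90.5% / 89.5% | 91.2% / 90.4% |

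Under uniform accrual the largest significant HR was 0.732, and the 536th event fell at 3.49 years. That matches the plan's own statement that "at 3.5 years since the first patient is randomized the hazard ratio is 0.70". The lower mean HR at the interim is what the plan expects, since "the average hazard ratio is expected to become more null (closer to 1) over time".

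**5. Table 4.** Its 69% is near the 67.5% that the 0.09% test gives at a fixed HR of 0.70. It lies between that and the simulated 76%, and it is far from the 28% to 38% that a 0.66 boundary gives. The models as stated do not reproduce it exactly. Table 4's null figure of 0.22% raises no issue. The plan says "Design properties were determined via simulation with 100,000 replications", so the Monte Carlo standard error is √(0.0022 × 0.9978/100,000), about 0.015 percentage points, and 0.22% is about one standard error from 0.206%.

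**The case against.** The strongest reply is that the operative rule is already in the text: a stratified log-rank test at one-sided 0.09%. The HR column is defined as following from alpha, so a committee working from the text would compute a p-value and never use 0.66. Crossing leads only to consideration of early release, and Section 11.5 says the clinical benefit on RFS will also be judged on size of effect, survival and toxicity. If the interim were skipped under the contradictory sentence, the final test at 0.32% would merely be conservative against the 0.4% allocated.

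All of that stands, and it limits the weight of the point. It also means the 38% is the chance of landing where the two rules disagree, not the chance of a wrong decision, which would further require someone to use the printed cell. The simulation is unstratified and without dropout and does not reproduce Table 4's 69%, although the fixed-HR calculation gives a similar 40%. The formula also misses the first OS interim by 0.014.

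None of this explains 0.66 or reconciles the two statements about the interim.

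**Conclusion.** Both parts hold. The sentence excluding overall-population RFS from interim testing contradicts the rest of Section 11.5 and Tables 3, 4 and 6, and it is the outlier. Table 6's interim threshold does not follow from its own alpha and events: it should be about 0.73, and 0.66 corresponds to an alpha roughly 58 times stricter (0.0009/0.0000155).

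The practical effect is confined to the early-release decision. Using 0.66 would cut the chance of crossing at the interim from about 68% to 76% down to about 28% to 38%, depending on whether a fixed HR of 0.70 or the plan's cure models are used. Overall RFS power falls by about one point. The two-look one-sided type I error is 0.206% under the 0.09% rule and 0.160% with 0.66 as the boundary. The threshold result rests only on 1:1 allocation and the standard log-rank variance; the probabilities rest on the simulation assumptions given above. This should be fixed, but it does not undermine the design.

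**What to change.** - Limit the sentence on interim testing to the PD-L1 positive subgroup, so that it excludes formal interim tests of RFS and OS there and is silent on overall-population RFS.
- Change Table 6's interim efficacy threshold to about 0.73, or state the alpha and event count that give 0.66.
- Add one line saying that the one-sided 0.09% stratified log-rank test governs and that the HR column is derived from it.
- Look up Table 4's 69% in the existing design simulation and state the interim HR it assumes. This is a secondary check.
- Table 3 expected the interim in mid-2018, and the documents do not say whether it took place. If it did, add a short note recording which rule was applied.

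The cost is one sentence, one table cell, one clarifying line and a look-up. Alpha, sample size and analysis method do not change.

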11.3 Overall survival (OS) and relapse-free survival (RFS) design assumptions

OS and RFS estimates from S0008 indicate that a proportion of patients may be long-term survivors in the sense that they will not be observed to relapse or die during the follow-up period planned for the study. It is further assumed that there are no differences in OS or RFS between the treatment regimens in the control arm.

An exponential cure rate model fit to OS on the HDI arm of S0008 indicated that 40% of patients were long-term survivors and that median OS for patients who were not long-term survivors was 3.01 years (null hypothesis). The null OS model is written that the OS at year t is equal to $0.40 + 0.60 \cdot \exp(-0.23t)$. For sample size calculations, it is assumed that OS with pembrolizumab will also follow an exponential cure rate model, but with 45% of patients long-term survivors and a median OS for non-long term survivors of 3.96 years (alternative hypothesis). The alternative OS model is written that the OS at year t is equal

to $0.45+0.55*\exp(-0.175t)$. This corresponds to an average hazard ratio (HR, average of 10,000 simulated hazard ratios from the Cox model) of 0.73 from a Cox proportional hazards model at 100% OS events (374 events at Study Year 5).

An exponential cure rate model fit to RFS on the HDI arm of **S0008** indicated that 35% of patients were long-term survivors and that median RFS for patients who were not long-term survivors was 1.03 years (null hypothesis). The null RFS model is written that the RFS at year t is equal to $0.35+0.65*\exp(-0.67t)$. For sample size calculations, it is assumed that RFS with pembrolizumab will also follow an exponential cure rate model, but with 41% of patients long-term survivors and a median RFS for non-long term survivors of 1.44 years (alternative hypothesis). The alternative RFS model is written that RFS at year t is equal to $0.41+0.59*\exp(-0.48t)$. This corresponds to an average hazard ratio (HR) of 0.70 from a Cox proportional hazards model at 100% RFS information.

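### Table 4's 69% chance of stopping RFS for efficacy at the interim does not follow from the stated models and one-sided 0.09% boundary, which give about 76%; the boundary that was simulated needs confirming

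*Combined protocol and SAP*

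**What the plan says.** Section 11.3 gives an exponential cure model for RFS in each arm. For control, "35% of patients were long-term survivors and that median RFS for patients who were not long-term survivors was 1.03 years", written as 0.35 + 0.65·exp(−0.67t). For pembrolizumab, the model is "with 41% of patients long-term survivors and a median RFS for non-long term survivors of 1.44 years", written as 0.41 + 0.59·exp(−0.48t). It ties the average HR of 0.70 to full RFS information. The design has 1:1 randomization, 2.5 years of accrual and 1,240 eligible patients (sections 11.1 and 11.3).

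Section 11.5 says "100% of expected RFS is 536 events" and places one interim at "75% of RFS events (402 RFS events calculated across both arms under the alternative". The interim efficacy test is "with a one-sided alpha=0.09" percent, and Table 6 repeats the level as "0.09% (one-sided". The final test is at the "two-sided 0.32% level (one-sided 0.16% level". Section 11.5 says the design properties come from simulation with 100,000 replications.

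Under the alternative, Table 4 gives 69% for "Probability stop for efficacy at interim analysis" and 90% for a positive result. Under the null it gives 0.22% for a positive result. Table 6 prints an interim HR threshold of 0.66.

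**The concern.** The 69% is presented as the simulated output of a fully specified design, so it should be reproducible. It is not, although its neighbours are. A gap of 7 points is far too large to be Monte Carlo error with 100,000 replications.

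Two things are at stake. First, the chance of going on to the final RFS analysis without an efficacy stop is stated as 31% (100 − 69), when the printed boundary gives about 24%. Second, if the figure came from a boundary other than the printed one, the plan leaves open which boundary applies to a co-primary endpoint. An interim one-sided p-value between 0.00045 and 0.0009 would cross under one reading and not under the other, and section 11.5 makes crossing the trigger for the DSMC to consider early release of RFS.

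**Working it through.** **Inputs.** The two cure models (section 11.3), 620 patients per arm (half of 1,240), accrual over 2.5 years taken as uniform, a log-rank test at the 402nd and 536th events, and one-sided levels of 0.09% and 0.16% (section 11.5).

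**Can the plan's own figures be reproduced?** With 20,000 simulated trials:

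| Quantity | Plan | Simulation |
|---|---|---|
| RFS, probability of a positive result | 90% | 90.3% |
| RFS, average HR at 536 events | 0.70 | 0.695 |
| RFS, futility stop under the alternative | <1% | <1% |
| OS, efficacy stop at first interim | 28% | 28.5% |
| OS, efficacy stop at second interim | 19% | 19.8% |
| OS, probability of a positive result | 86% | 85.5% |
| **RFS, efficacy stop at interim** | **69%** | **76%** |

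The last row is the exception. Separate runs of 8,000 to 20,000 trials gave 75.5% to 76.3% with an unstratified test, and 75.4% with 24 strata. The Monte Carlo standard error is 0.3 points at 20,000 trials. Varying the accrual length and ramp-up, or using 1,378 patients, gave 74.4% (accrual over 3 years) to 78.0% (steep ramp-up).

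**Analytic check.** The model's average HR at 402 events is about 0.68, lower than the 0.70 at full information. This agrees with the remark in section 11.5 that the average HR moves toward 1 over time. With z = 3.121 for one-sided 0.09%:

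P(cross) = Φ(−ln(HR)·√402/2 − 3.121)

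- HR 0.681 (simulated mean at the interim): Φ(3.852 − 3.121) = 76.7%.
- HR 0.70 held constant: Φ(3.576 − 3.121) = 67.5%.

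**What would give 69%?**

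- *0.09% taken as two-sided* (0.045% one-sided, z = 3.320), same cure models, 402 events: 69.3% unstratified and 69.0% stratified, with other runs up to 70.0%. Total power stays at about 90%.
- *A calendar cut at 2.5 years*: 70.0%, but that is only about 360 events, not 402.
- *A constant HR of 0.70*: 67.5%, which is not the stated model and is a poorer match.

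**Which reading fits the alpha?** The one-sided probability, under the null, of crossing at either look (correlation √0.75) is 0.206% with 0.09% one-sided at the interim, and 0.178% with 0.045%. The RFS allocation is 0.4% two-sided, or 0.20% one-sided, and Table 4 prints 0.22%. The one-sided reading is closer to both.

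**Table 6 threshold.** The HR at the boundary is exp(−2z/√d). For the final look, exp(−2 × 2.948/√536) = 0.775, matching the printed 0.78. For the interim, exp(−2 × 3.121/√402) = 0.73 as one-sided, or exp(−2 × 3.320/√402) = 0.72 as two-sided. The printed 0.66 would need z = −ln(0.66)·√402/2 = 4.17. An interim cut at 0.66 would be crossed in only about 39% of trials, so it does not explain 69% either.

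**The case against.** The strongest objection concerns the remedy. A reader might infer that 69% is simply wrong and that 76% should be written in its place. The documents do not support treating that as settled: the printed 69% and 90% both reproduce if 0.09% was simulated as a two-sided level, so the error could lie in the label, or in the sidedness used in the simulation. A reader might equally infer that 69% matches no boundary at all. That is also too strong, because the two-sided reading matches it. This part of the objection stands. What it does not do is reconcile the text as printed: 69% and one-sided 0.09% at 402 events cannot both be right.

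A second objection is that the figure drives nothing. No decision rule uses it. Section 11.5 says the trial is overpowered for RFS and sized for OS, and the tables warn that analysis timing may vary. This stands as to importance. The documents do not show the DSMC or sponsor relying on the 69%.

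A third is that the cell is one symptom of a wider lack of clarity about the RFS interim. Table 6's 0.66 is inconsistent with the stated alpha, and a later sentence in section 11.5 says RFS will have no formal interim testing. That is fair, and argues for reconciling the interim RFS boundary in one pass.

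**Conclusion.** The point holds as a minor correction. Under the stated cure models, 402 events and a one-sided 0.09% log-rank boundary, the chance of an efficacy stop at the RFS interim is about 76% (74% to 78% over the accrual patterns and sample sizes tried), against 69% in Table 4. The one assumption added to the stated inputs is the accrual pattern, and none of the patterns tried brings the figure down to 69% at 402 events.

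The likely source is 0.09% handled as two-sided, but this is an inference. The repeated one-sided label, the 0.4% allocation and the printed 0.22% null error all favour the one-sided boundary, so 76% is the likelier correct entry. Overall RFS power of 90% and the sample size are unaffected.

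**What to change.** Confirm from the simulation code which interim RFS boundary was used.

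- If one-sided 0.09% stands, re-run at that boundary and print about 76% in Table 4. This changes one cell and leaves design and alpha alone.
- If 0.09% was meant as two-sided, correct the label in the section 11.5 text and in Table 6, and recompute the null error in Table 4 (0.178% by the calculation above, against the printed 0.22%).

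In either case, replace or explain the 0.66 interim threshold in Table 6: the stated alpha at 402 events gives about 0.73, or 0.72 if two-sided. The cost is one simulation re-run and a few table or label entries.

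### Section 11.5: two efficacy HR thresholds (RFS interim 0.66, OS first look 0.67) do not match the alpha and event count beside them, and Table 2's 2.1% OS null probability does not match the stated levels

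*Combined protocol and SAP*

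**What the plan says.** Section 11.5 makes the efficacy decisions by p-value: "Tests of the null hypothesis will be done using the log-rank test", stratified by the randomization factors. The levels are:

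- RFS, overall population: "One formal interim analysis of the overall population RFS endpoint is scheduled at approximately 75% of RFS events" (402 events), "with a one-sided alpha=0.09"%, with a final test at one-sided 0.16% (536 events).
- OS, overall population: two interim looks, each "with a one-sided alpha=0.125"%, and a final test "at the two-sided 3.6% level (one-sided 1.8% level) in order to account for interim analyses". Tables 1 and 5 put the looks at 206, 299 and 374 events.

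Tables 5 and 6 then restate each rule as a hazard ratio, explained as "HR threshold = HR that will correspond to a significant p-value based on alpha level", and add that efficacy HRs below the threshold will be significant. The printed efficacy thresholds are 0.67, 0.70 and 0.81 for OS, and 0.66 and 0.78 for RFS.

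Table 2 gives an 86% probability of a positive OS result under the alternative and 2.1% under the null. Its footnote cites a two-sided level of 3.7%, ignoring futility. On origin the section says only: "Design properties were determined via simulation with 100,000 replications".

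Further down, the same section states: "There will be no formal interim testing of RFS (overall or PD-L1 positive subgroup"), which conflicts with the RFS interim analysis it has already scheduled.

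**The concern.** Each table row prints an alpha, an event count and a threshold, and by the tables' own definition the first two fix the third. If a row disagrees with itself, the committee has two rules for one look.

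For RFS, an interim HR between 0.66 and 0.73 meets the 0.09% test but not Table 6, so a crossed boundary could be read as not crossed. That range contains 0.70, the average RFS hazard ratio assumed in Section 11.3. For OS the direction reverses: a first-look HR between 0.656 and 0.67 crosses Table 5 but does not reach 0.125%.

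Table 2 raises a separate doubt. The overall OS test has 1.85% one-sided (3.7% two-sided). From the document a reader cannot tell whether 2.1% is a reporting error or the true error rate of whatever rule was simulated.

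**Working it through.** **Inputs.** Alphas: Section 11.5 text and Tables 5 and 6. Event counts: Tables 1, 3, 5 and 6. Allocation 1:1: Section 11.3. For the second OS look the 11.5 text prints 399 events; 299 is used here because Tables 1 and 5 give it and 0.80 × 374 = 299.2.

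**Formula.** With 1:1 allocation the variance of the log HR is about 4/d, so threshold = exp(−2z/√d), where z is the one-sided normal quantile and d the number of events.

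| Look | One-sided alpha | z | d | Computed | Printed |
|---|---|---|---|---|---|
| OS second | 0.125% | 3.023 | 299 | 0.705 | 0.70 |
| OS final | 1.8% | 2.097 | 374 | 0.805 | 0.81 |
| RFS final | 0.16% | 2.948 | 536 | 0.775 | 0.78 |
| **OS first** | 0.125% | 3.023 | 206 | **0.656** | **0.67** |
| **RFS interim** | 0.09% | 3.121 | 402 | **0.732** | **0.66** |

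The second-look OS futility threshold also reproduces: 0.73 × exp(2 × 1.96/√299) = 0.916, printed 0.92. The formula therefore recovers the plan's other numeric thresholds in Tables 5 and 6. Table 7 prints no event count and is not assessed.

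**What the two printed cells imply.** Inverting, z = −ln(HR) × √d/2.
- 0.66 at 402 events: z = 4.166, one-sided p = 0.0016%. It would fit 0.09% only at about 226 events. Halving the alpha gives 0.718 and the Freedman approximation 0.731, so neither explains 0.66.
- 0.67 at 206 events: z = 2.874, p = 0.20%. Even 0.665, the lowest value that rounds to 0.67, gives p = 0.17%. Freedman gives 0.652.

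**Check against the plan's operating characteristics.** The probability of crossing a cut-off c at true hazard ratio θ is Φ([ln c − ln θ] × √d/2).
- RFS interim, c = 0.66: 28% at θ = 0.70 and 38% at θ = 0.68. With c = 0.732: 67% and 77%. Table 4 prints 69%. A 69% stop needs a cut-off of 0.735 (θ = 0.70) or 0.714 (θ = 0.68); with 0.66 it would need θ of about 0.63.
- Simulating the Section 11.3 RFS cure models (1,240 patients, 2.5 years' uniform accrual, unstratified log-rank, 6,000 replicates) gives an average HR of 0.68 at 402 events. The stop probability is 75.4% with the 0.09% rule and 37.0% with HR < 0.66.
- OS first look under the OS cure models, simulated the same way: 27.7% with the 0.125% rule and 34.0% with HR < 0.67. Table 2 prints 28%. Simulated OS power is 86.0%, as in Table 2.

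Both comparisons favour the stated alphas over the printed cut-offs.

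**OS null probability.** Take the three log-rank statistics as trivariate normal with correlation √(dᵢ/dⱼ): 0.830 (206/299), 0.742 (206/374) and 0.894 (299/374).
- Stated levels 0.125%/0.125%/1.8%: 1.84% one-sided, 3.68% two-sided, which agrees with the 3.7% footnote.
- Stated interim levels with the printed final cut-off 0.81: 2.12%.
- All three printed cut-offs (0.67/0.70/0.81): 2.15%.
- Plain sum of the levels, the maximum under any correlation: 0.125 + 0.125 + 1.8 = 2.05%.

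At 100,000 replications the Monte Carlo standard error is √(0.0184 × 0.9816/100,000) = 0.04 percentage points, so 2.1% lies about 6 standard errors above 1.84%. Futility stopping can only lower the figure. Likewise, two looks at 0.125% give a null probability of 0.21% for an early OS efficacy stop, where Table 2 prints 1%.

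**The case against.** The strongest reply is that nothing operational depends on these cells. The text fixes the rule as a log-rank test at a stated alpha, the captions of Tables 5 and 6 warn that actual timing may differ, and crossing the RFS boundary only leads the committee to consider early release. The RFS error is conservative, so any HR below 0.66 is indeed significant. The OS gap is 0.014 on the HR scale, and the accepted cells 0.81 (p 2.08% against 1.8%) and 0.78 (p 0.201% against 0.16%) are slightly liberal too. For 2.1%, the section does name simulation as the source, and the footnote's 3.7% is right. The cure-model simulation gives 75.4% for the RFS interim stop, not Table 4's 69%.

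Much of this limits the weight of the point without removing it. Alpha governs and the error-rate plan is intact. But a caveat about timing cannot explain a mismatch at the event counts printed in the same row. The cells 0.81 and 0.78 are correct two-decimal roundings, whereas 0.66 and 0.67 are not. Non-proportional hazards do not rescue 0.67: under the OS cure model the Cox HR at the log-rank boundary averages about 0.653. The gap between 75.4% and 69% means the sponsor's simulation is not fully recreated, but 37% is much further from 69%. Naming simulation does not say which rule was simulated, and that is what is needed to interpret 2.1%.

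**Conclusion.** Wrong as written, and worth fixing. The RFS interim threshold should be 0.732, not 0.66; the OS first-look threshold should be 0.656, not 0.67; and the null probability of a positive OS result under the stated levels is 1.84%, not 2.1%. The RFS cell matters most, because the discrepant range covers the effect the trial was designed around. The OS cell is a small error beyond rounding. The origin of 2.1% is unknown: a simulation run on rounded thresholds is possible (2.12% or 2.15%), but the document does not show it.

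These results assume the printed alphas and event counts are the intended ones, 1:1 allocation, 299 events at the second OS look, and the usual large-sample variance for the log-rank test. The plan's own 69% and 28% support taking the alphas as intended. The contradiction over whether RFS has a formal interim test is separate from the arithmetic, but it leaves the standing of Table 6's interim row unclear.

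**What to change.** 1. After confirming the alphas and event counts, print 0.732 for the RFS interim in Table 6 and 0.656 for the first OS look in Table 5. Use three decimals, since 0.66 at 206 events is already p = 0.143%; on the same basis the other efficacy thresholds are 0.705 and 0.805 (OS) and 0.775 (RFS).
2. Add one sentence under both tables: the stratified log-rank p-value at the stated alpha decides, and the HR thresholds are approximate values at the planned event counts.
3. Rerun the Table 2 null simulation with the stated levels, report the result (about 1.84% expected, with an early efficacy stop of about 0.21%), and state which rule produced 2.1%.
4. Reconcile the sentence denying formal interim RFS testing with the scheduled RFS interim analysis.

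The cost is a few table cells, one simulation run, one added sentence and one reconciled sentence. No test, alpha, sample size or patient procedure changes.
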